6.2 Site approval and activation

On receipt of the signed Clinical Trial Agreement, approved delegation of responsibilities log and staff contact details, written confirmation will be sent to the site PI. The CI will notify the PI in writing of the plans for site initiation. Sites will not be permitted to recruit any patients until a letter for activation has been issued. The CI will be responsible for issuing this after an NCTU green light to recruit process has been completed.

The site must conduct the trial in compliance with the protocol as agreed by the Sponsor and, by the regulatory authority(ies) (as appropriate), and which was given favourable opinion by the Research Ethics Committee (REC). The PI or delegate must document and explain any deviation from the approved protocol, and communicate this to the trial team at NCTU.

A list of activated sites may be obtained from the research fellow.

6.3 Participants

6.3.1 Eligibility Criteria

Patients with previous major amputation or active osteomyelitis have been excluded. This is because it prevents the comparison of temperature differences between the feet (standard care). This is either due to the possibility of bilateral inflammation confounding the results or the absence of a comparator limb.

6.3.1.1 Participant selection

There will be **NO EXCEPTIONS** (waivers) to eligibility requirements at the time of randomisation. Questions about eligibility criteria should be addressed PRIOR to attempting to randomise the participant.

The eligibility criteria for this trial have been carefully considered and are the standards used to ensure that only medically appropriate participants are entered. Participants not meeting the criteria should not be entered into the trial for their safety and to ensure that the trial results can be appropriately used to make future treatment decisions for other people with similar diseases or conditions. It is therefore vital that exceptions are not made to these eligibility criteria.

Participants will be considered eligible for enrolment in this trial if they fulfil all the inclusion criteria and none of the exclusion criteria as defined below.

6.3.1.2 Participant Inclusion Criteria

- Participants who are willing and have capacity to give informed consent.
- People with diabetes as diagnosed by the WHO criteria
http://www.who.int/diabetes/publications/diagnosis_diabetes2011/en/
- Age 18 years or over
- New or suspected diagnosis of acute CN (no previous incidence of acute CN within the last 6 months on the same foot) treated with off-loading
- Understand written and verbal instructions in English

6.3.1.3 Participant Exclusion Criteria

- People who have received a transplant and others receiving immunosuppressant therapy or using long term oral glucocorticoids other than in the routine management of glucocorticoid deficiency. Participants on a low doses of oral glucocorticoids (<10mgs for ≤7 days) are eligible to participate in the study.
- Participation in another intervention study on active CN
- Contra-indication for MRI
- Treatment for previous suspected CN on the same foot in the last 6 months
- Suspected or confirmed bilateral active CN at presentation
- Active osteomyelitis at randomisation
- Previous contralateral major amputation
- Inability to have an MRI scan
- Patients receiving palliative care

6.3.1.4 Eligibility Criteria for Individuals Performing the Interventions

The clinicians working in the diabetic foot clinic will be asked to become members of the research team and as such will be carrying out the trial. They will be identified on the delegation log and must have received study specific training to ensure consistency in the way the monitoring is completed.

6.3.1.5 Co-enrolment Guidance

Participants who are involved in other studies where there is a known effect or contraindication to investigation of CN will also be excluded. The CI should be contacted to discuss any concerns over eligibility prior to recruitment. If participants are already involved in trials with exposure to radiation then their eligibility for inclusion in this trial will need to be raised with the CI and discussed by the TMG.

6.3.1.6 Screening Procedures and Pre-randomisation Investigations

Written informed consent to enter and be randomised into the trial must be obtained from participants, after explanation of the aims, methods, benefits and potential hazards of the trial and **BEFORE** any trial-specific procedures are performed or any blood is taken for the trial. The only

procedures that may be performed in advance of written informed consent being obtained are those that would be performed on all patients as part of standard care.

6.4 Interventions - Arm A and Arm B

All patients will attend the secondary care clinic for fortnightly visits or as per current standard care, outlined in 6.4.5. Additional visits maybe arranged depending on clinical need. Procedures which are part of standard care will be completed according to trial specific WPD.

In this trial a standardised assessment of serial temperature measurements will be carried out. This will be completed according to trial WPD. The temperature of both feet will be recorded at intervals of 5 minutes starting at the initial removal of the off-loading device for up to 15 minutes. This will assess acclimatisation and the period of equilibration needed for stabilisation of temperature.

- 1) Following initial removal of the off-loading device
- 2) Following a 5 minute resting period
- 3) Following a 10 minutes resting period
- 4) Following a 15 minutes resting period

The sites where the temperature will be recorded reflect the current classification tool developed by Sanders and Frykberg⁴⁸;

1. distal and proximal interphalangeal joints, metatarsophalangeal, tarsometatarsal joints
2. naviculo-cunieform joints, talo-navicular joint
3. calcaneocuboid joint
4. ankle joint, subtalar joint
5. calcaneus

One X-ray will be additional to standard care this will be taken 6 months post remission. Participants who do not reach this time point within the 18 month intervention and follow-up period will not have this X-ray. This will enable the progression of foot deformity to be assessed. If a participant becomes pregnant during the study they will not have the additional X-ray and will be excluded from the analysis of the progression of foot deformity. Two members of the research team will independently evaluate the images to assess the progression of foot deformity. Inter-rater reliability will be assessed. The X-rays will be anonymised prior to evaluation to ensure the researcher is blinded to participant number and site. [The anonymised scans will also be randomly sequenced to avoid bias.](#)

To allow comparison all X-ray and MRI images will be taken as per trial WPD.

The participants will also be asked to complete the following questionnaire/assessments. These will be completed at randomisation, 3 monthly until remission (3, 6, 9 and 12 months), 1 month after remission, and at 6 months post remission;

- 1) Pain in the foot and/or leg measured using a numerical 0-10 visual analogue scale
- 2) Health related quality of life assessed by the Medical Outcomes Short-Form Health Questionnaire (SF12)

- 3) Psychological health status measured using the Hospital Anxiety and Depression Scale (HADs)
- 4) EQ-5D-5L

Patients will be issued with a patient diary at every visit and ask to complete it over the next fortnight. At each visit the old patient diary will be collected and a new one provided until the next visit.

6.4.1 Arm A (Intervention – Standard Care and Serial MRIs)

Immobilisation discontinued on the basis of MRI defined disease resolution at 3, 6, 9 or 12 months

In the intervention arm participants will receive additional MRIs at 3, 6, 9 and 12 months. Patients randomised to serial MRI will not undergo further MRI once remission has been diagnosed i.e. if remission is diagnosed at 6 months the MRI at 9 and 12 months will not occur.

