1.3 Structured trial summary

Primary Registry and Trial Identifying Number	ISRCTN – No to be confirmed
Date of Registration in Primary Registry	Date when trial was officially registered in the primary registry.
Secondary Identifying Numbers	IRAS: 222668 NNUH R&D Number: UEA Reference: R202374
Source of Monetary or Material Support	NHIR Clinical Doctoral Fellowship ICA-CDRF-2015-01-050
Sponsor	Norfolk and Norwich University Hospitals NHS Foundation Trust,
Contact for Public Queries	[name] [contact] [name] NIHR Clinical Doctoral Fellow School of Health Sciences University of East Anglia
Contact for Scientific Queries	[name] [contact] [name] NIHR Clinical Doctoral Fellow School of Health Sciences University of East Anglia
Short Title/Acronym	CADOM
Scientific Title	A randomised feasibility study to assess the use of serial magnetic resonance imaging to reduce treatment times in Charcot neuroarthropathy in people with diabetes
Countries of Recruitment	United Kingdom
Health Condition(s) or Problem(s) Studied	The assessment of Charcot neuroarthropathy in people with diabetes
Intervention(s)	Intervention Serial use of MRI at 3, 6, 9 and 12 months to identify disease resolution and thus discontinue immobilisation in addition to standard care

	
Standard Care Immobilisation discontinued on the basis of clinical remission determined by skin temperature measurement (Standard Care)

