5.1.1 Explanation for choice of comparators

Participants will be randomised to one of two arms;

(a) Serial use of MRI at 3, 6, 9 and 12 months to identify disease resolution and thus discontinuation of immobilisation plus standard care (**intervention**)

(b) Immobilisation discontinued on the basis of clinical remission determined by skin temperature measurement, which triggers an MRI (**standard care**)

The complications of the diabetic foot, osteomyelitis and CN, have well described appearances on MRI. The use of MRI in determining a diagnosis of CN in the early stages of disease when no signs are evident on plain radiology is well recognised⁴⁷. It has recently been suggested that the findings on MRI should be adopted as the criterion standard for establishing disease activity and remission in CN³⁸. This is because MRI has the greatest potential to allow monitoring the effect of treatment since it shows bone marrow oedema (inflammation). The majority of clinicians use the measurement of temperature described earlier, despite the increasing availability of MRI.

The literature suggests that MRI maybe superior to clinical techniques in determining the timing of termination of immobilisation. A small study demonstrated that mean healing time was significantly related to the baseline contrast medium uptake. A significant correlation between intensity of bone marrow oedema in MRI and clinical measures of soft tissue oedema and pain was found in another study⁴¹. A further small study suggested that semi quantitative scoring for bone marrow oedema and fracture on MRI might be useful in monitoring treatment of CN⁴².

There is a need for the use of MRI to be formally evaluated in a trial. This trial aims to explore the feasibility of using serial MRI in an attempt to reduce the duration of immobilisation of the foot.

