6.4.4 Compliance and Adherence

6.4.5 Concomitant Care

All patients will receive treatment as standard for their CN regardless of randomisation into this trial. This will be recorded on the eCRf and form part of the data for this study;

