6.7.2 The “active phase” – up to 12 months

These visits will take place in the participant’s usual place of care (secondary care). Participants will attend for fortnightly visits. Standard care and study specific procedures will be carried out and recorded on the eCRF.

Study Specific Procedures

- The temperature assessment as per the WPD
- The participant diary will be collected and another issued for participants to complete over the next 2 weeks, until their next study visit.

In both arms remission will be defined as an absence of sub-chondral bone marrow oedema on MRI, as reported by a specialist musculoskeletal radiologist and/or the absence of clinical signs and symptoms of CN. The clinical team will interpret the results of the MRI report to determine remission. As per standard care at this point patients will have a foot and ankle X-ray.

Participants who develop bilateral CN during the study can continue in the trial. The trigger to arrange the MRI in the standard care arm will be based on the absence of signs and symptoms of active CN as assessed by the clinical team.

Patients randomised to A (Intervention – Serial MRI)

Patients randomised to the intervention group will have an MRI of their foot and ankle three monthly (at 3, 6, 9 and 12 months) until the CN has settled. Where possible the scan should be scheduled to coincide with study visits to minimise the number of additional hospital visits.

For participants in the intervention arm if the MRI report indicates to the clinical team that the CN is not in remission participants will continue in the active phase of the study, up to a maximum of 12 months.

Patients randomised to B (Standard Care)

Patients randomised to the standard care will undergo an MRI once the temperature difference between their feet is $\leq 2^{\circ}\text{C}$ on two separate occasions at least four weeks apart.

For participants in the standard care arm if the MRI report indicates to the clinical team that the CN is not in remission participants off-loading will be recommenced. Participants will continue in the follow up phase as per the trial protocol.

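### The protocol describes Arm A both as serial MRI added to a temperature-based stopping rule and as stopping at scheduled scans, and gives no single answer for a participant who meets the temperature rule between scans

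*Protocol*

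**What the plan says.** **Sections that make Arm A additive.** The structured summary (1.3) gives the intervention as "Serial use of MRI at 3, 6, 9 and 12 months to identify disease resolution and thus discontinue immobilisation in addition to standard care". Section 5.1.1(a) likewise has "discontinuation of immobilisation plus standard care", and the heading of 6.4.1 pairs standard care with serial MRIs. Sections 1.3 and 6.11.5.1 describe standard care as ending immobilisation on clinical remission judged by skin temperature. Section 5.1.1(b) adds the scan: "clinical remission determined by skin temperature measurement, which triggers an MRI". Section 6.4.5 states "All patients will receive treatment as standard for their CN regardless of randomisation into this trial".

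**Sections that tie Arm A to the scan dates.** The text of 6.4.1 reads "Immobilisation discontinued on the basis of MRI defined disease resolution at 3, 6, 9 or 12 months". Section 6.7.2 gives Arm A three-monthly scans and states the temperature trigger under Arm B alone, as does 6.4.2. The timeline in 6.6 shows intervention-arm MRIs at baseline and at weeks 12, 26, 40 and 52. Section 6.11.5.1 repeats the summary's description of Arm A but drops the reference to standard care.

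**What counts as remission.** Section 6.7.2 defines it for both arms by a clear MRI and/or no clinical signs and symptoms. Section 6.7.4 says that in both arms the MRI confirms it.

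**Measurement and outcome.** Sections 6.4, 6.6 and 6.7.2 have foot temperatures taken at the fortnightly visits in both arms. Section 6.11.4.1 names days with immobilisation as the suggested primary efficacy outcome, to be analysed by Cox regression. Section 1.3 lists an estimate of effect size among the feasibility outputs.

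**The concern.** If Arm A is standard care plus serial MRI, and standard care is itself a rule for ending immobilisation, Arm A can only add stopping opportunities to those of Arm B. If Arm A stops at scheduled scans, it replaces an opportunity that recurs every fortnight with four dates, and it could lengthen immobilisation even if MRI were the better marker. These are different interventions.

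The situation will arise in practice. Staff in an open-label trial will see Arm A participants meet the temperature rule between scans, and a clinician could find support in the protocol for scanning then or for waiting. A mixture of the two would blur both the effect estimate and the variability estimate that the definitive trial is meant to inherit.

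**Working it through.** The protocol states no figure on this point, so there is none to reproduce. The check is how far the two readings differ when the protocol's own intervals are used.

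**Inputs from the protocol**
- Visits every 14 days (6.7.2).
- Temperature rule held for at least 4 weeks, i.e. 28 days (6.4.2, 6.7.2).
- Arm A scans at weeks 12, 26, 40 and 52 (6.6). The longest gap is 26 - 12 = 14 weeks.
- Active phase capped at 12 months (6.4.2).

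**Assumptions, because the protocol gives no figure**
- The distribution of time to resolution.
- The lag between MRI clearing and temperature settling.
- The wait for a triggered scan.

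**Closed form.** Suppose clearing is spread evenly between scans and both signs settle together.
- Scheduled scans only: mean wait = 91.3 / 2 = 45.7 days.
- Temperature rule: mean wait = 14 / 2 + 28 = 35 days.
- Arm A minus Arm B with scheduled scans only: 45.7 - 35 = +10.7 days.
- With both triggers, Arm A stops at the earlier of the two routes, so the difference cannot be positive.

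A temperature lag L or a scan wait W lengthens only the temperature route, so the scheduled-only difference becomes 45.7 - (35 + L + W). It reaches zero when L + W is about 10.7 days.

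**One participant.** Both signs settle at day 100. The next fortnightly visit is day 112, and the trigger is met at 112 + 28 = day 140, when Arm B stops. Arm A stops at the 6-month scan, about day 183 (+43 days), on the scheduled reading, or at day 140 (0 days) with both triggers.

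**Simulation.** 400,000 resolution times per setting were drawn from a Weibull distribution with shape 1.5 to 2 and median 26 to 52 weeks, capped at 52 weeks. Arm B stops at the first fortnightly visit with temperature settled plus 4 weeks, and not before MRI resolution. The entries are mean differences, Arm A minus Arm B, in weeks.

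| Temperature relative to MRI | Wait for triggered scan | Scheduled scans only | Both triggers |
|---|---|---|---|
| 4 weeks before | none | +2.6 to +5.3 | 0 |
| together | none | +0.8 to +1.7 | -0.4 to -0.8 |
| together | 2 weeks | about -0.1 | negative |
| 2 weeks after | none | about -0.1 | negative |
| 4 weeks after | none | -0.9 to -1.9 | -1.1 to -2.5 |
| 8 weeks after | none | the readings agree, negative | the readings agree, negative |

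**Second distribution.** Log-normal clearing times were used with log-SD 0.4 and medians of 4, 6 and 9 months, repeating an unclear confirmatory scan every 28 days (assumed). With both signs settling together, the difference is +8.0 to +15.2 days with scheduled scans only and -4.0 to -7.2 days with both triggers. In that setting 39% to 64% of Arm A participants would stop earlier if both triggers applied. The scheduled-only difference crosses zero at a lag of about 10 to 15 days, in line with the closed form.

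**The case against.** The strongest reply is that the operational sections agree with one another. Sections 6.4.1 (text), 6.4.2, 6.6 and 6.7.2 all give scheduled scans to Arm A and the triggered scan to Arm B. Section 6.4.2 calls the triggered scan an additional MRI, which suggests that it too is added to standard care and does not come into Arm A with it. On that view the standard-care label in 5.1.1(b) is just the name of the comparator arm. Trial working documents and study-specific training (6.4, 6.3.1.4) may settle the matter at site level, so divergence between sites is a possibility and not a demonstrated fact. Section 6.4.5 is also weak evidence, because no list of what standard care contains follows it in the text at hand.

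Much of this stands, and 6.4.5 should carry little weight. It does not remove the additive wording in 1.3, 5.1.1(a) and the 6.4.1 heading, or the statements in 1.3 and 6.11.5.1 that standard care ends immobilisation on temperature. Section 6.12.3.1 also describes MRI to confirm resolution after temperature assessment as standard care. The and/or definition of remission in 6.7.2 would let Arm A stop between scans on clinical grounds.

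A reader might go further and infer that Arm A participants are bound to wait for the next scan. The documents do not say so: 6.4.1 does not restrict stopping to the four dates in terms, 6.7.2 leaves the determination of remission to the clinical team, and 7.1 lets the clinician depart from protocol treatment.

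**Conclusion.** The point holds at moderate weight. The protocol defines the intervention it is piloting in two ways and does not settle whether the temperature trigger applies in Arm A between scheduled scans. With temperature and MRI settling together and no wait for the triggered scan, the choice moves the mean difference from about +0.8 to +1.7 weeks to about -0.4 to -0.8 weeks.

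A reader might infer that the choice reverses the direction of the effect in general. The documents do not support that. The reversal depends on assumed distributions and on a temperature lag and scan wait that together stay below roughly 10 to 15 days. A lag or a wait of 2 weeks brings the scheduled-only difference to about -0.1 weeks, and at an 8-week lag the readings coincide. If temperature settles 4 weeks before MRI, the contrast is a lengthening against zero, which is not a reversal either. The protocol reports neither the lag nor the wait.

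The stakes are limited too. This is a 60-participant feasibility study (6.8), not powered for clinical outcomes (5.2), with between-group efficacy exploratory (6.11.4.1). Among the feasibility outcomes the main exposure is the estimation of outcome parameters for the definitive trial.

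**What to change.** Reconcile sections 1.3, 5.1.1, 6.4.1, 6.7.2, 6.7.4 and 6.11.5.1 and the timeline in 6.6, so that they give one answer on whether the temperature trigger applies in Arm A between scheduled scans. The investigators should decide which answer that is; this review takes no position on it.

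Add one eCRF field that records, for every stop of immobilisation in both arms, what triggered it: scheduled scan, temperature trigger or other. Report its distribution by arm next to the effect and variability estimates, so that the definitive trial can see which intervention was delivered.

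The cost is protocol wording and one data field. There is no change to sample size or visit schedule. The number of scans changes only if the investigators decide that the trigger applies in Arm A.

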6.4.2 Arm B (Control – Standard Care and one additional MRI)

Immobilisation discontinued on the basis of clinical remission determined by skin temperature measurement and MRI. In the standard care arm participants will receive one additional MRI when the temperature measurements, X-ray and/or signs and symptoms indicate to the clinical team that the foot is in remission.

A temperature difference of $\leq 2^{\circ}\text{C}$ which is maintained or improves on two separate consecutive occasions for a period of ≥ 4 weeks will be the indicator to arrange the second MRI, to confirm the diagnosis of remission.

If participants in either arm of the trial have not reached remission at the end of the 12 month active phase of the study they will exit the study. Ongoing standard care will be provided by their clinical team.

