which did use this protocol achieved disease resolution/remission in 25 of 28 patients referred with acute CN, with a re-exacerbation rate of zero after one year follow up²⁸. Other researchers have used different protocols to assess temperature, one study used eight sites on each foot, with three readings taken at each site and an average calculated³⁵. Another study used the highest reading in each foot³⁶. In a number of studies disease resolution/remission has been defined as a temperature difference of $\leq 2^{\circ}\text{C}$ on just one occasion. Other studies have required a temperature difference of $\leq 2^{\circ}\text{C}$ to be maintained for two³⁷ or more consecutive appointments²³. These differences could extend treatment times by 2-6 weeks as patients need to attend two or more clinic appointments before the foot is judged to be in resolution/remission.

The complications of the diabetic foot, osteomyelitis and CN, have well described appearances on MRI. The use of MRI in determining a diagnosis of CN in the early stages of disease when no signs are evident on plain radiology is well recognised³⁸. However serial MRI as a tool to monitor for signs of disease remission is not widely used in routine clinical practice and was not recommended in the systematic review published in 2015¹⁵. Recently it been suggested that the findings on MRI should be adopted as the criterion standard for establishing disease activity and remission³⁹. MRI has the greatest potential to monitor the effect of treatment since the findings are a more direct reflection of the degree of tissue and bone inflammation. The literature suggests that MRI maybe superior to clinical techniques in determining the timing of termination of immobilisation. A small study demonstrated that mean healing time was significantly related to the baseline contrast medium uptake⁴⁰. A significant correlation of intensity of bone marrow oedema in MRI and clinical measures of soft tissue oedema and pain was found in another study⁴¹. Another small study suggested that semi-quantitative scoring for bone marrow oedema and fracture on MRI might be useful in monitoring treatment of CN⁴².

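### Sections 6.4.2 and 6.7.2 word the control-arm trigger for the remission MRI differently, and the difference can shift control-arm days with immobilisation

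*Protocol*

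**What the plan says.** Section 6.4.2 (Arm B) has two statements. The first gives control participants an MRI "when the temperature measurements, X-ray and/or signs and symptoms indicate to the clinical team that the foot is in remission". The next paragraph makes the indicator a temperature difference of ≤2°C "which is maintained or improves on two separate consecutive occasions for a period of" ≥4 weeks.

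Section 6.7.2 restates the rule for Arm B as a difference of ≤2°C "on two separate occasions at least four weeks apart". It does not require the occasions to be consecutive, or the difference to be held or improved between them. The same section makes the absence of signs and symptoms the trigger for control participants who develop bilateral CN.

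On the schedule, 6.7.2 says "Participants will attend for fortnightly visits" and lists "The temperature assessment as per the WPD" among the procedures of that phase. Section 6.4 is looser: "All patients will attend the secondary care clinic for fortnightly visits or as per current standard care".

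Section 6.11.4.1 names days with immobilisation as the suggested primary efficacy outcome, to be analysed by Cox regression. Section 6.5.1 lists estimates for the sample size of a definitive trial among the feasibility outcomes.

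**The concern.** The trigger is the gate to ending immobilisation in the control arm. Section 6.4.2 bases discontinuation on temperature and MRI, so the scan cannot confirm remission before it has been arranged. Arm A is scanned at fixed times (3, 6, 9 and 12 months), so a difference in how this rule is read acts on the control arm only.

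If two sites, or two clinicians, read the rule differently, control participants with the same temperature record can be scanned on different dates. Control-arm days with immobilisation would then mix rules. So would the variability and effect estimates that the feasibility trial is meant to hand on to the definitive trial.

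**Working it through.** **1. The wordings on the visit grid.** Visits are every 2 weeks with a temperature at each. Two consecutive visits span 1 × 2 = 2 weeks. A span of 4 weeks needs three visits (weeks 0, 2 and 4). Section 6.4.2 therefore has two interpretations:
- (a) two consecutive visits, leaving the 4-week element unmet;
- (b) three readings, all ≤2°C, at weeks 0, 2 and 4.

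Section 6.7.2 gives (c): two readings ≤2°C at least 4 weeks apart, whatever lies between.

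**2. A record that separates them.** Readings are ≤2°C at week 10, above 2°C at week 12 and ≤2°C at week 14. Under (c) the MRI is triggered at week 14. Under (a) and (b) it is not.

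**3. Stable readings.** If every reading stays ≤2°C once reached, the weeks from the first such reading to the trigger are (a) 2, (b) 4 and (c) 4. So (b) and (c) coincide, and (a) is 2 weeks earlier.

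**4. Fluctuating readings, simple model.** Let p be the chance that a reading is ≤2°C at any visit (assumed; not in the protocol). Mean weeks from the first visit considered = 2 × (E − 1), where E is the expected number of visits:
- (a) E = (1 + p)/p²
- (b) E = (1 + p + p²)/p³
- (c) E = 2/p + 1

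For p = 0.8: (a) 2 × (2.81 − 1) = 3.6; (b) 2 × (4.77 − 1) = 7.5; (c) 2 × (3.5 − 1) = 5.0.

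| p | (a) | (b) | (c) | (b) − (c) |
|---|---|---|---|---|
| 1 | 2.0 | 4.0 | 4.0 | 0 |
| 0.9 | 2.7 | 5.4 | 4.4 | 1.0 |
| 0.8 | 3.6 | 7.5 | 5.0 | 2.5 |
| 0.7 | 4.9 | 10.8 | 5.7 | 5.1 |
| 0.6 | 6.9 | 16.1 | 6.7 | 9.4 |

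With much fluctuation (a) loses its lead over (c): 6.9 against 6.7 weeks at p = 0.6. A constant p is crude because the foot is cooling, so the next step lets it cool.

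**5. Fluctuating readings, declining temperature.** Section 5.1 gives presenting differences of 5.1 to 14.7°C. Assumed: a linear fall to 0.5°C over 26 to 52 weeks, staying there afterwards; normal reading error with SD 0.5 to 0.8°C; fortnightly visits; 20,000 simulated participants per scenario. Mean delay of (b) relative to (c):

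| Presenting difference | Mean delay, weeks |
|---|---|
| 5.1°C | 1.5 to 7.6 |
| 10°C | 0.3 to about 3 |
| 14.7°C | 0.1 to 1.7 |

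At 14.7°C the median delay is 0 in every scenario. With a smaller error SD of 0.2 to 0.3°C, the mean delay at 5.1°C falls to 0.2 to about 2 weeks. A further requirement that successive readings do not rise is left out of these figures, because its effect depends heavily on how it is coded.

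**6. The non-temperature route.** The and/or list in the general sentence of 6.4.2 permits X-ray or signs and symptoms without a temperature criterion, and states no duration. Section 6.7.2 gives a signs-and-symptoms trigger only for bilateral CN. The text does not settle whether that route is open to all control participants.

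**The case against.** Several points on the other side have force.

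- **The rules are close.** Both use ≤2°C, two occasions and a 4-week element. A reader might infer that the 6.4.2 rule can never be met. That goes too far: a third reading is already being taken, so holding ≤2°C at weeks 0, 2 and 4 satisfies its sense. Section 6.4 also allows visits at the standard-care interval, and with 4-weekly visits two consecutive occasions do span 4 weeks.
- **A separate third trigger.** A reader might count the general sentence in 6.4.2 as one. It reads equally well as an introduction to the temperature rule that follows. What stands is that its scope is unclear.
- **Size.** Section 5.1 says "These differences could extend treatment times by 2-6 weeks", and it is tempting to apply that here. It compares published definitions requiring one occasion with those requiring two or more. Both control-arm temperature rules already require two, so the figure does not size this discrepancy.
- **Consequence.** The trigger only arranges an MRI, so a shifted trigger need not move days with immobilisation one for one. Efficacy is exploratory and unpowered, and staff receive training meant to secure consistency. The trial's working documents (WPDs) are not at hand and might fix the rule, although the protocol cites them for how temperature is assessed, not for this trigger. Nothing in the protocol shows that sites do read the rule differently. Stratifying allocation by centre does not help, because it cannot remove a shift confined to one arm.

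These points limit the size and certainty of the effect. They do not make the two sections say the same thing.

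**Conclusion.** Sections 6.4.2 and 6.7.2 do not state the same rule, and 6.4.2 does not fit the fortnightly schedule without interpretation. That follows from the text alone.

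The size is conditional. With stable readings the difference is nil between 6.7.2 and the three-reading interpretation, and 2 weeks if 6.4.2 is taken as two visits. With fluctuating readings the mean difference between 6.7.2 and the three-reading interpretation is about 0.1 to 7.6 weeks. The upper end needs the lowest presenting difference, the slowest decline and the larger reading error. The decline, the 0.5°C floor and the reading error are assumptions; only the presenting range is the protocol's.

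A reader might infer that any between-arm difference would reflect wording and not MRI. The protocol does not support that. It supports only that differing interpretations can shift the control-arm value of the suggested primary efficacy outcome, and with it the planning estimates for the definitive trial. That is enough to justify a correction.

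**What to change.** Reconcile 6.4.2 and 6.7.2 into one identically worded trigger, chosen by the clinical team; this review does not say which rule is right. The wording should state:
- the number of readings and the span they must cover;
- whether an intermediate reading above the threshold restarts the count;
- what the held-or-improved condition demands of successive readings, if it is kept;
- whether the signs-and-symptoms route applies outside bilateral CN.

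Record on the eCRF the date on which the trigger was met and its basis.

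Optionally, derive from the temperatures already collected the date on which each wording was met, up to the date of remission. After remission, visits become monthly (6.7.4), so for participants released under a looser reading the date under a stricter one may not be observable. That should be stated with the results.

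The cost is a wording amendment and two eCRF items, with an optional derived variable. No visits or scans are added.
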